# 4.5.2 Visit 1, Visit 2, and End of Study Visit

The following data will be collected for all enrolled participants at each follow-up time point:

- Medication use;
- Strength measurements using QMA, HHD, and MMT;
- 10-MWT;
- 1-Minute Sit-to-Stand Test;

Template No.: RWI\_TP\_EPI0011 Revision 2 Reference: RWI\_WI\_EPI0005

ARMGO Pharma, Inc. RYR1-RM Study Version 4.0 dated 10-SEP -2024 Protocol/Study No.: CL-EPI-001

Page 41 of 64

- 4SCT;
- PROMIS Questionnaires (at End of Study Visit only);
- IPAQ (at End of Study Visit only);
- Full physical, neurological, and functional examination (at End of Study Visit only);
- Syde® device removal (at Visit 1 only);
- Symptom Diary (to be completed daily between Screening Visit and End of Study Visit); and
- AE/SAE.

#### 4.5.3 Study Withdrawal/Discontinuation

The following data will be collected for all enrolled participants at the time of discontinuation:

- Date of discontinuation; and
- Reason for discontinuation.

Once the participant informs the PI that they wish to withdraw or discontinue from the study, then no additional information or data will be captured for that participant.

#### 4.5.4 End of Study

The End of Study is defined as the date of the last query resolution i.e all data has been recorded in the electronic case report form and all data queries resolved to allow database lock to occur. This will ensure that all data is available to answer the research questions in the study protocol. This definition will be used across all participating sites.

#### 5. DEVICES

The use of digital tools, such as wearable devices and other remote sensors, allows for the continuous, objective, and sensitive measurements of a participant's functional ability during daily life. Validated class I medical wearable devices have been used in clinical trials for assessing functional outcomes in daily life for participants with neuromuscular disorders (48) including clinical trials of participants with Duchenne Muscular Dystrophy and can be used in both ambulant and non-ambulant participants with movement disorders. (49)

Participants will be provided with a wearable device to collect daily physical activities. The purpose of the wearable device is to accurately measure the movement and activity levels of

Template No.: RWI\_TP\_EPI0011 Revision 2 Reference: RWI\_WI\_EPI0005

ARMGO Pharma, Inc. RYR1-RM Study Version 4.0 dated 10-SEP -2024 Protocol/Study No.: CL-EPI-001

Page 42 of 64

the participant during normal daily living, outside of investigational site visits. The Syde® device consists of 2 sensors (and a docking station). It is a Class I medical device manufactured by Sysnav. There are no foreseeable risks and minimal inconveniences to the participants who will wear it. Participants will wear one sensor on each ankle.

As the wearable device battery requires recharging daily after use, the sensors will not be worn at night. Site personnel, the participant, and parents/caregivers will be trained on the correct use of the device. The device will be fitted on the participant in the clinic prior to the Stair Climb Test, in order to ensure that it is working well, which can be assessed as participant climbs the stairs. The device would be removed when participants take part in activities which could damage the sensors or where the device could be in contact with water. Detailed user instructions are provided in the wearable device participant manual and quick start guide.

The wearable device will be worn on both ankles daily for 30 ( $\pm$ 3) days (to be taken off only at night before sleeping) from Screening Visit [Syde® device fitting] to Visit 1 [Syde® device removal]).

The quantity of data recording will be closely monitored by Sysnav and communicated to the sites to maintain an adequate participant compliance throughout the recording period, until the end of the study. The recorded data will then be checked for accuracy, completeness, relevance, and consistency, before the last step of data analysis which includes the process of using algorithms to generate the Syde® clinical variables.

The wearable device will not be worn during clinic visits, but participants will resume use immediately following completion of in-clinic tests. Subjects must return the wearable device in the event of screen failure, early termination, or after study completion.

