#### f) 4 Stair Climb Test (4SCT)

Lastly, the 4SCT will be used to assess leg muscle power. The test equipment consists of a stopwatch and a flight of 4 stairs with rail. The participant will stand at the base of the stairs and will be required to ascend the stairs as fast as possible. Timing will start after the tester instructs the participant to start climbing and will stop when both participant's feet reach the top step. (15, 37)

This test will be administrated at Screening, Visit 1, Visit 2, and End of Study Visit, including three trails per visit. Stair climb power will be calculated using the following formula: power =  $[(body weight in kg) \times (9.8 \text{ m/s}^2) \times (stair height in meter)]/(time in seconds). (15, 37)$  The raw scores of the 4SCT will be expressed as Watts and will also be described as deviations from normative values. (38)

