# 4.5.1 Screening Visit

The following data will be collected at the Screening Visit for all enrolled participants (listed in the order in which they will be collected during the visit):

- Informed consent;
- Inclusion/Exclusion (including MMT to assess muscle/motor function deficit, 10-MWT to assess ability to walk, and FVC to assess pulmonary dysfunction);
- Demographics (medical records);
- Medical history (medical records);
- Medication use (medical records);
- Vital signs and ECG (medical records or primary data collection; note that FVC will be evaluated as part of the assessment of the exclusion criteria);
- Strength measurements using QMA and HHD (note that MMT will be conducted at the start of the Screening Visit as part of the assessment of the inclusion criteria);
- 1-Minute Sit-to-Stand Test;
- 4SCT:
- Full physical, neurological, and functional examination;
- PROMIS Questionnaires;
- IPAO:
- Syde® device fitting;
- Symptom diary (initiation); and
- AE/SAE.

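### The protocol gives conflicting instructions on whether ankle sensors are worn during the Screening stair climb, so the baseline test condition is not fixed

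*Protocol*

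**What the plan says.** Section 5 (Devices) states: "The device will be fitted on the participant in the clinic prior to the Stair Climb Test". The stated reason is to confirm that the device works, "which can be assessed as participant climbs the stairs". The device is therefore on the ankles during the Screening climb.

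Section 4.5.1 (Screening Visit) says its items are "listed in the order in which they will be collected during the visit". In that list the 4 Stair Climb Test (4SCT) comes first. The clinical examination, the PROMIS questionnaires and the IPAQ follow, and only then the item "Syde ® device fitting". The Screening list in the Synopsis runs in the same sequence.

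Later in Section 5 comes "The wearable device will not be worn during clinic visits", followed by "participants will resume use immediately following completion of in-clinic tests".

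Section 4.5.2 places device removal at Visit 1 and lists it after the 4SCT, but that list is not declared to be a sequence.

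On the test itself, Section 4.4.1.1 f) says: "This test will be administrated at Screening, Visit 1, Visit 2, and End of Study Visit". Each visit has three trials. Section 3 (Table 1) places the stair climb under the primary objective. Section 4.4.1.1 makes Screening the baseline and asks for one fixed order of tests for everyone at every site. Section 6.2.1 plans changes from Screening to each follow-up visit and changes between consecutive follow-up visits.

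**The concern.** Two current operative instructions give opposite sensor conditions for the same test at the same visit. One site may follow Section 5 and another Section 4.5.1, and each would be complying with the protocol.

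The test affected supplies a baseline. If sensors are on at Screening and off later, any influence they have on climbing speed becomes part of the change from Screening. It cannot be separated from a real shift after the first visit. Section 2 says the repeated measurements are there to show how many are needed for a stable baseline and to describe variability for Phase II, so an avoidable difference in conditions at the first visit touches the purpose of the study. An analysis plan could not restore the common condition afterwards, because the problem arises when the data are collected.

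The condition could also differ between participants at one visit. Under Section 4.2.1, willingness to wear the device is needed only for the exploratory analysis, so some participants may never have sensors on.

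**Working it through.** The protocol gives no figure on this point and none can be recomputed. The check sets the instructions side by side and follows each combination through the four visits.

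**Step 1. Sensor status implied by each instruction**

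- Section 5, fitting sentence: Screening on.
- Section 4.5.1, ordered list: Screening off.
- Section 5, not-worn sentence: off at any visit it covers. This certainly includes Visit 1; whether it includes Screening is open.
- Section 4.5.2, removal listed after the 4SCT: Visit 1 on, if a site reads the list as a sequence.
- After removal at Visit 1: Visit 2 and End of Study off.

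**Step 2. The possible combinations for a device wearer**

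| Case | Screening follows | Visit 1 follows | Screening | Visit 1 | Visit 2 | End of Study |
|---|---|---|---|---|---|---|
| A | Section 5 fitting | Section 5 not-worn | on | off | off | off |
| B | Section 4.5.1 order | Section 5 not-worn | off | off | off | off |
| C | Section 5 fitting | Section 4.5.2 as listed | on | on | off | off |
| D | Section 4.5.1 order | Section 4.5.2 as listed | off | on | off | off |

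Only case B keeps one condition throughout.

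**Step 3. What enters the planned changes**

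Let d be the difference in measured stair climb power, sensors on minus sensors off, for one participant. The documents give no value for d, and it may be close to zero. A change from visit i to visit j picks up d × (status at j − status at i), with on = 1 and off = 0.

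| Case | Screening to V1 | Screening to V2 | Screening to End | V1 to V2 | V2 to End |
|---|---|---|---|---|---|
| A | −d | −d | −d | 0 | 0 |
| B | 0 | 0 | 0 | 0 | 0 |
| C | 0 | −d | −d | −d | 0 |
| D | +d | 0 | 0 | −d | 0 |

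For example, Screening to Visit 1 in case A is d × (0 − 1) = −d.

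The three trials within a visit share one sensor condition, so summarising across them would not remove d. If a proportion w of the analysed participants are in case A with a common d, and all others have one condition throughout, the mean change from Screening shifts by −w × d.

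**Step 4. What this settles**

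Which changes are affected, and in which direction, depends on the combination a site happens to follow. The text permits more than one, so the test condition is not standardised.

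**The case against.** The strongest reply concerns the not-worn sentence. It goes on to speak of resuming use, and one resumes only what has begun. It can therefore be read as governing visits after fitting, with Screening outside its scope. On that reading the two sentences in Section 5 are compatible. This stands, so a reader who infers that all three statements exclude one another goes too far. It does not rescue the protocol, because the ordered list in Section 4.5.1 is about the Screening Visit itself and still contradicts the fitting sentence.

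Three other stronger readings also fail.

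- A reader might infer that all three changes from Screening are biased in the same direction. That is case A only. It needs the device to be off for the Visit 1 climb, and the list in Section 4.5.2 leaves room for the opposite. It also needs d to differ from zero. In case A the two planned changes between follow-up visits are unaffected.
- A reader might infer that the sensor condition is confounded with a learning effect the study sets out to measure. Section 2 states the expected learning effect for the QMA endpoints, not for the stair climb. What remains is the general aim of a stable baseline and known variability.
- A reader might infer that clinic climbs contaminate the daily-life recording. A few four-step climbs in about 30 days of wear are minor, and Section 5 has the recorded data checked for relevance before the device variables are generated.

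It is also fair to say that the 4SCT is one of several additional tests, that the study is descriptive, and that Section 5 describes the sensors as causing little inconvenience. These points limit the weight of the finding but do not remove the contradiction.

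**Conclusion.** Wrong as written, low severity. What is certain is that the fitting sentence in Section 5 and the ordered list in Section 4.5.1 cannot both be followed. The sensor condition for the Screening 4SCT is therefore not fixed, although Section 4.4.1.1 asks for standardised testing.

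The consequence is conditional. Device wearers at sites that follow Section 5 would have a sensors-on baseline, with Visit 2 and End of Study sensors-off, and Visit 1 too if the not-worn sentence is applied. Any resulting shift ranges from none (case B, or d = 0) to −d in every change from Screening (case A). The size of d is unknown and may be small. The 20 participants are a ceiling on enrolment, and the number affected is at most the number who wear the device. The other primary-objective tests are not shown to be affected.

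The conclusion rests on reading Section 4.5.1 as a binding sequence, which it says it is, and on the sensors staying on during the climb, which the stated function check implies.

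**What to change.** Reconcile the Synopsis Screening list, Sections 4.5.1 and 4.5.2, and the two sentences in Section 5, so that all scored 4SCT trials are done under one stated sensor condition at every visit. The simplest way is to:

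- keep the Section 4.5.1 order, so that the device is fitted after the scored Screening climbs;
- amend the fitting sentence in Section 5 to match, with the function check done outside the scored trials;
- state in Section 4.5.2 that removal at Visit 1 comes before the 4SCT;
- say which visits the not-worn sentence covers.

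The cost is protocol wording and a line in site training. A separate unscored climb is one way to do the function check, but it is optional and adds effort at Screening for participants with proximal weakness. A rule on when the analysed recording starts is likewise optional and is not needed to cure the contradiction.

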# 6. STATISTICAL METHODS

# 6.1 Sample Size

The study plans to enrol up to 20 participants. This sample size is based on the number of participants that will be feasible to recruit at the participating sites. Given the explorative and descriptive nature of this study and the rarity of the target population, formal sample size calculations were not performed. Accordingly, the primary focus of the study is on measuring and describing the study endpoints in the target population rather than on statistical hypothesis testing.

Template No.: RWI\_TP\_EPI0011 Revision 2 Reference: RWI\_WI\_EPI0005

ARMGO Pharma, Inc. RYR1-RM Study Version 4.0 dated 10-SEP -2024 Protocol/Study No.: CL-EPI-001

Page 43 of 64

# 6.2 Data Analyses

#### **6.2.1** General Considerations

All computations and generation of tables, listings, and data for figures will be performed using SAS® version 9.2 or higher (SAS Institute, Cary, NC, USA).

Prior to database lock, a detailed, finalized SAP will be completed and approved. The SAP will contain a more comprehensive description of the methodology for the statistical analyses than outlined in this protocol. The SAP will provide full details of the analyses, the data displays, and the algorithms to be used for data derivations.

Continuous variables will be described using descriptive statistics of central tendency (median and mean) and dispersion (standard deviation, interquartile range, maximum and minimum values). Categorical variables will be summarized as counts and proportions of the total study population. The 95% confidence interval will be presented for estimates of means and proportions. Descriptive statistics for both continuous and categorical variables will be based on participants with non-missing responses to the variable. Frequencies and percentages of missing values in each variable will be reported.

Whenever applicable, the endpoints will be summarized by each visit and across the overall study period (e.g., average endpoint across study visits). Furthermore, the absolute change in the endpoints between (i) Screening and each follow-up visit, and (ii) between each consecutive follow-up visit will be calculated and summarized with descriptive statistics.

# 6.2.2 Planned Analyses

#### 6.2.2.1 Primary Objective Analysis

Muscle strength endpoints measured through the QMA, HHD, and MMT and functional test scores (including 10-MWT, 1-Minute-Sit-to-Stand Test, and 4SCT) will be summarized using descriptive statistics, as detailed in Section 6.2.1 (including absolute values and changes). These endpoints will be described as both raw scores and deviations from normative values in healthy individuals (if available).

The variability of the primary study endpoints between repeated measurements and/or visits will be assessed using graphical methods and correlation coefficients.

Further details about the statistical methodology, including any comparison to available normative data will be included in the SAP.

Template No.: RWI\_TP\_EPI0011 Revision 2 Reference: RWI\_WI\_EPI0005

ARMGO Pharma, Inc. RYR1-RM Study Version 4.0 dated 10-SEP -2024 Protocol/Study No.: CL-EPI-001 Page 44 of 64

# 6.2.2.2 Secondary Objective Analysis

The PROMIS Fatigue, PROMIS-PF, and IPAQ questionnaires will be scored according to their manual instructions (see Section 4.4.1.2). PRO endpoints assessed through the PROMIS Fatigue, PROMIS-PF, and IPAQ questionnaires and the symptom diary will be summarized using appropriate descriptive statistics, as outlined in Section 6.2.1.

Demographic and clinical characteristics of participants and data collected through the diary will be summarized with descriptive statistics, as outlined in Section 6.2.1. AE endpoints recorded throughout the study will also be summarized through descriptive analysis.

#### 6.2.2.3 Explorative Objective Analysis

Explorative endpoints will be summarized using descriptive statistics, as appropriate.

Additional exploratory analyses may be performed and outlined in the SAP prior to the data analysis.

#### **6.2.3** Handling of Missing Data

It is optimal to prevent missing data, to the extent possible, through strategies set forth in the design and conduct of a study. For the current study, we will aim to minimize missing information by:

- Ensuring that primary variables of interest are those that are routinely collected as part of real-world clinical care and are available via medical charts, physician and/or participant/caregiver reporting, as appropriate;
- Collecting only critical data elements (i.e., variables aligned with the study objectives) to minimize site/participant burden;
- Including "not applicable" or "not done" on CRFs to differentiate missing values; and
- Training of sites and data abstractors regarding data collection and setting reporting windows around a target time point.

Should missing data occur, the data will be analysed as they are recorded in the study database. The number of missing values for data elements will be reported, and the impact of missing data on the analysis and the pattern of the missing information will be assessed. Full details on the handling of missing data will be described in detail in the SAP (e.g., approach to dealing with missing data on the individual questionnaire items in the scoring of the questionnaires).

Template No.: RWI\_TP\_EPI0011 Revision 2 Reference: RWI\_WI\_EPI0005

ARMGO Pharma, Inc. RYR1-RM Study Version 4.0 dated 10-SEP -2024 Protocol/Study No.: CL-EPI-001 Page 45 of 64

# **6.2.4** Limitations of Research Methods

#### 6.2.4.1 Selection Bias

Given the small size of the study and the use of a non-random sampling approach, the recruited sample of participants may not be representative of the target population; hence, the results may not be generalizable to the wider population.

# 6.2.4.2 Confounding Bias

Due to the observational nature of the study, any observed changes in the endpoints or relationships between different study endpoints could be explained by unmeasured confounding factors not accounted for in the analysis.

# 6.2.4.3 Information Bias

The presence of missing data may introduce bias to the study results. To mitigate this bias, the patterns of missing data will be analysed, and potential imputation approaches will be discussed with the study team, depending on the nature and quantity of the missing information.

Self-report bias (e.g., social desirability, recall bias) could affect the PRO measures. This risk will be mitigated by using validated questionnaires, whenever possible, and by providing detailed instructions and guidance to participants on the completion of the PRO questionnaires.

Measurement bias, which could result from variations in the weight of the participants' extremities, the force applied by the examiner, and the strength of the examiner, could affect the measurement of the endpoints. This will be mitigated by ensuring adequate training for examiners taking the measurements.

Systematic errors in reporting data into the eCRFs could be another source of measurement bias. This will be mitigated through implementing rigorous data quality and monitoring procedures for the data collected by the eCRF and by providing rigorous training to the study team.

#### 6.2.4.4 Statistical Power

The study has limited power to detect statistical differences due to the small size of the sample. Any confidence intervals and p-values from statistical hypothesis tests will be considered descriptive and should be interpreted with caution.

Template No.: RWI\_TP\_EPI0011 Revision 2 Reference: RWI\_WI\_EPI0005

ARMGO Pharma, Inc. RYR1-RM Study Version 4.0 dated 10-SEP -2024 Protocol/Study No.: CL-EPI-001

Page 46 of 64

# 6.3 Data Reporting

# 6.3.1 Progress Reports

Not applicable.

# 6.3.2 Annual/Interim Analyses and Reporting

As this is a non-interventional observational study the data will be assessed on an ongoing basis for accuracy and completeness, however full reporting will only be done when all participants have completed, and the study is considered closed.

# 6.3.3 Final Analyses and Reporting

A final study report will be generated after all data collection is complete. The final report will encompass all planned analyses, including a description of the complete study population, as described above and in the SAP.

#### 7. STUDY MANAGEMENT

This study will be performed by IQVIA with guidance, input, review, and approval of the Sponsor., including development of materials, recruitment, training and management of sites, electronic data capture (EDC) and data management and analysis.

## 7.1 Data Entry/Electronic Data Capture

All data will be collected and entered directly into the EDC system. Data for the study may be entered directly into the EDC system by the study staff or pre-populated using electronic health record data and later verified by the study staff.

All sites will be fully trained in using the online data capture system, including eCRF completion guidelines and help files. Sites will manage entering extracted participant data into a secure internet-based EDC registry database via the eCRF. Investigators and site personnel will be able to access their account with a username and password. All eCRFs should be completed by designated, trained personnel or the study coordinator, as appropriate. In most cases, the eCRF should be reviewed, electronically signed, and dated by the principal investigator. All changes or corrections to eCRFs are documented in an audit trail and an adequate explanation is required.

Syde® will have 2 watch-like devices. The watch-like devices contain a three-axis accelerometer, a three-axis gyroscope, and a three-axis magnetometer that record, respectively, the linear acceleration, the rotation rate (angular velocity), and the magnetic field in the 3 dimensions of space. These sensors are just plugged on the docking station every night by

Template No.: RWI\_TP\_EPI0011 Revision 2 Reference: RWI\_WI\_EPI0005

ARMGO Pharma, Inc. RYR1-RM Study Version 4.0 dated 10-SEP -2024 Protocol/Study No.: CL-EPI-001

Page 47 of 64

participants. If a participant authorizes automatic data upload, then data gets uploaded automatically to Sysnav cloud storage. If a participant does not authorize automatic data upload, or if automatic data upload is not possible then data gets stored on an encrypted USB drive within the docking station, retrieved by the clinical site at the end of the recording period and shipped back to Sysnav. It is then uploaded by Sysnav authorized personnel to the cloud.

